5.8.1 Analysis of Adverse Events

The number and proportion of patients will be summarized separately for the week 16 treatment period, the follow-up period and overall study period, described in [Section 3.3](#). The incidence tables will present by primary SOC (sorted by internationally agreed order for the dupilumab group), HLT, HLT and PT sorted in alphabetical order for each treatment group and selected subgroup, including the number (n) and percentage (%) of patients experiencing a TEAE. Multiple occurrences of the same event in the same patient will be counted only once in the tables within a treatment phase. The denominator for computation of percentages is the safety population within each treatment group.

TEAEs will also be summarized by severity and relationship to IMP for each treatment group, presented by primary SOC and PT.

The time to first TEAE of special interest (AESIs) during the week 16 treatment period will be assessed by Kaplan-Meier estimates (K-M plot). The time is defined as the date of first event – the date of first dose + 1. Patients without an event will be censored at the end of 16-week treatment period. Graphs of cumulative incidence rate over time will be presented by treatment group.

Listings will be provided for all TEAEs, SAEs, death and TEAEs leading to permanent treatment discontinuation by treatment group and patient. Flags will be used to indicate on-treatment death.

The following variables will be included in the listing:

- Patient ID
- Treatment group
- Age/sex/race
- SOC
- HLGT
- HLT
- PT
- Verbatim Term
- AE start date and end date/ongoing
- AE Duration
- Relationship of AE to study drug: unrelated or related
- Action taken: drug interrupted, dose reduced, drug withdrawn, drug not changed, dose increased, or not applicable
- Severity: using a 3-point scale (mild, moderate, or severe)
- Outcome: recovered or resolved, recovered or resolved with sequelae, recovering or resolving, not recovered or not resolved, fatal or unknown

Overall TEAE summary

The overall summary of TEAEs will be provided with number and proportions of patients with any:

- TEAE
- TEAE related to study drug
- TEAE by severity
- Serious TEAE
- TEAE of special interest (AESI)
- TEAE leading to death
- TEAE leading to permanent treatment discontinuation

AESI:

- Anaphylactic reactions
- Systemic or extensive hypersensitivity reactions
- Malignancy
- Helminthic infections
- Suicide-related events
- Blepharitis (severe or serious or lasting ≥ 4 weeks)
- Any type of conjunctivitis (severe or serious or lasting ≥ 4 weeks)
- Pregnancy of a female patient entered in a study as well as pregnancy occurring in a female partner of a male patient entered in a study with IMP/NIMP
- Symptomatic overdose (serious or nonserious) with IMP/NIMP

[Appendix 10.5](#) provides a list of AESIs search criteria.

TEAE Incidence

Number and proportions of patients reporting TEAEs will be summarized for the following TEAEs:

- TEAEs
 - TEAEs by SOC/PT
 - TEAEs by SOC/HLGT/HLT/PT
 - TEAEs by SOC/PT with PT $\geq 5\%$ in any treatment groups
 - TEAEs by severity by SOC/PT
 - TEAEs by relationship to IMP assessed by the investigator by SOC/PT
 - TEAE of special interest by category and PT
- Serious TEAEs
 - Serious TEAEs by SOC/PT
 - Serious TEAEs by SOC/HLGT/HLT/PT
 - Serious TEAEs related to study drug as assessed by the investigator by SOC/PT
- TEAEs leading to permanent discontinuation of study treatment by SOC/HLGT/HLT/PT
- TEAE leading to death (death as an outcome on the AE CRF page as reported by the investigator) by SOC/HLGT/HLT/PT

Death

- Number (%) of patients who died by study period (TEAE, on-study) and reasons for death summarized on the safety population by treatment received
- Death in nonrandomized patients or randomized and not treat patients

5.8.2 Analysis of Clinical Laboratory Measurements

Laboratory measurements include clinical chemistry, hematology and urinalysis results, and will be converted to standard international units and US conventional units. Summaries of laboratory variables will include:

- Descriptive statistics of baseline laboratory test results and change from baseline to each visit
- Number and percentage of patients with a treatment-emergent PCSA
- Shift tables based on baseline normal/abnormal and other tabular and graphical methods may be used to present the results for laboratory tests of interest.

Listing of all laboratory parameters normal range, abnormal flag and treatment-emergent PCSA by patient and visit will be provided.

5.8.3 Analysis of Vital Signs

Summaries of vital sign variables will include:

- Descriptive statistics of baseline vital sign variable and change from baseline to each visit
- Number and percentage of patients with a treatment-emergent PCSA
- Shift tables based on baseline normal/abnormal and other tabular and graphical methods may be used to present the results for parameters of interest

Listings will be provided with flags indicating the treatment-emergent PCSA, depending on data.

5.8.4 Analysis of Physical Examination

Number and percentage of patients with abnormal physical examination will be summarized at baseline, end of treatment period and end of study by treatment group. A summary of treatment-emergent abnormal findings will be provided.

5.8.5 Analysis of 12-Lead ECG

Number and percentage of patients with abnormal ECG interpretation will be summarized at baseline, end of treatment period and end of study by treatment group.

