11.4.4 Analyses of safety data

The summary of safety results will be presented by treatment group. All safety analyses (includes reported TEAEs and other safety information as clinical laboratory evaluations, vital signs, and 12-lead ECG results) will be performed on the safety population using the following common rules:

- The baseline value is defined generally as the last available value before randomization.

For safety variables, two observation periods are defined:

- The pre-treatment period is defined as the time from signing the informed consent form (ICF) to before the first dose of IMP.
- The TEAE period is defined as the time from first dose of IMP (Day 1) to the end of the study.

The following definitions will be applied to clinical laboratory evaluations, vital signs and ECG.

- The potentially clinically significant abnormality (PCSA) values are defined as abnormal values considered medically important by the sponsor according to predefined criteria/thresholds based on literature review and defined by the sponsor for clinical laboratory tests, vital signs, and ECG.
- PCSA criteria will determine which patients had at least 1 PCSA during the on-treatment period, taking into account all evaluations performed during the on-treatment period, including unscheduled or repeated evaluations. The number of all such patients will be the numerator for the on-treatment PCSA percentage.

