1.3 Modifications from the Statistical Section in the Final Protocol

Modifications from the Amended protocol 1 (final protocol)

1. concomitant medication/procedure

Any concomitant treatment is considered from the first dose of study drug in the SAP instead of the time of informed consent in the protocol.

2. Potentially clinically significant abnormality (PCSA)

PCSA is applied to clinical laboratory evaluations and vital signs in SAP, while PCSA was applied to ECG as well in the protocol.

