4.5.3 Vital Sign Variables

The following vital signs parameters will be collected:

- Weight (kg) and height (cm)
- Respiratory rate (breaths/min)
- Heart rate (beats/min)
- Systolic and diastolic blood pressures (mmHg)
- Body temperature (°C)

Weight is determined at screening and baseline (Day 1), and Week 16 (EOT), Week 28 (EOS), ET and unscheduled visits. Height is only measure at screening. Other vital signs are collected pre-dose at every scheduled and unscheduled clinic visit.

4.5.4 12-Lead Electrocardiography (ECG) Variable

The ECG interpretation variable are dichotomized to normal and abnormal. Electrocardiograms will be performed before blood is drawn during visits requiring blood draws. A standard 12-lead ECG will be performed at screening, Week 16 (EOT), and Week 28 (EOS) or ET visits.

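### The SAP's ECG summary gives percent abnormal by visit and arm but compares no patient with his or her own baseline, so newly abnormal ECGs cannot be counted from it

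*SAP*

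**What the plan says.** Protocol 11.4.4 applies PCSA criteria to laboratory tests, vital signs and ECG, with a patient-level rule: "PCSA criteria will determine which patients had at least 1 PCSA during the on-treatment period".

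SAP 1.3 declares a change: "PCSA is applied to clinical laboratory evaluations and vital signs in SAP, while PCSA was applied to ECG as well in the protocol". It gives no reason. SAP Appendix 10.3 accordingly has no ECG thresholds.

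SAP 4.5.4 reduces the ECG to two levels, "The ECG interpretation variable are dichotomized to normal and abnormal", and sets the schedule: "A standard 12-lead ECG will be performed at screening, Week 16 (EOT), and Week 28 (EOS) or ET visits".

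SAP 5.8.5 then consists of one sentence: "Number and percentage of patients with abnormal ECG interpretation will be summarized at baseline, end of treatment period and end of study", by arm. Appendix 10.1 lists ECG under descriptive statistics only, with no supportive, subgroup or other analysis.

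The neighbouring sections go further. SAP 5.8.4, on physical examination, has a by-visit summary of the same form and adds: "A summary of treatment-emergent abnormal findings will be provided". SAP 5.8.2 and 5.8.3 plan treatment-emergent PCSA counts for laboratory tests and vital signs. Shift tables are optional there; for vital signs the text is "Shift tables based on baseline normal/abnormal and other tabular and graphical methods may be used to present the results for parameters of interest".

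**The concern.** ECG is a named safety endpoint in the protocol. For such an endpoint one usually wants to know how many patients had a normal tracing at baseline and an abnormal one later, by arm. The percentage abnormal at each visit does not say, because a new abnormality in one patient is offset by a resolved one in another. ECG is the only one of these four assessments for which the SAP plans no within-patient comparison with baseline.

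It looks like an omission. Physical examination has the same normal/abnormal coding and the same visits, and there the SAP adds the missing sentence. What is at stake is the descriptive safety report: readings that turned abnormal without meeting any adverse event criterion would not be counted as new in any planned table.

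**Working it through.** **Inputs.** The plan gives no ECG figure to reproduce. The only plan figure used is 80 patients per arm (SAP 2.2). The documents state no ECG abnormality rate, so every abnormal count below is an assumption. All 80 patients are taken to have a reading at both visits; missing readings would widen the ranges.

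**Formula.** For one arm, let n be the number of patients, b the number abnormal at baseline, w the number abnormal at Week 16, x the number newly abnormal and r the number resolved. Then:

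- w = b + x − r, so the table fixes only the net change, x − r = w − b.
- Since r cannot be negative, x is at least max(0, w − b).
- New cases must be abnormal at Week 16 and normal at baseline, so x is at most min(w, n − b).

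**Results with n = 80.**

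| b (assumed) | w (assumed) | Normal at baseline, n − b | Smallest x | Largest x |
|---|---|---|---|---|
| 4 | 4 | 76 | 0 | 4 |
| 8 | 8 | 72 | 0 | 8 |
| 16 | 16 | 64 | 0 | 16 |
| 8 | 12 | 72 | 12 − 8 = 4 | 12 |
| 16 | 12 | 64 | 0 | 12 |

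In the second row the largest value is 8/72 = 11.1% of those normal at baseline. One arm could have 8 new and 8 resolved abnormalities and the other none of either, and the two arms' columns would be identical.

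**Does another planned output fill the gap?**

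- *Adverse events.* SAP 4.5.1 records an ECG abnormality as an adverse event only if it causes symptoms, needs treatment or a consultation, leads to a change in or stop of study drug, is serious, or is of special interest. Those that begin or worsen after the first dose are tabulated by arm under SAP 5.8.1. Other new abnormal readings are not.
- *PCSA.* SAP 5.8 ties its treatment-emergent definition to PCSA, which it limits to laboratory tests and vital signs.
- *Visit windows.* SAP 6.4 still names ECG in its rule for choosing the readings that decide abnormal or PCSA values. That rule selects data; it creates no ECG table, and it no longer agrees with SAP 1.3 and 5.8.

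**Are the data there?** Yes. The screening ECG serves as baseline under SAP 6.1, and ECGs follow at Week 16 and at Week 28 or early termination.

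**The case against.** The strongest reply is that little is lost. The trial is randomised against placebo, so a net excess of abnormal ECGs on dupilumab would show as a difference between arms in percent abnormal at Week 16. For identical tables to hide 8 new cases in one arm and none in the other, all 8 baseline abnormalities must resolve in the first arm and none in the second, which is an extreme pattern. New abnormalities that meet the adverse event criteria are already counted. The removal of ECG from PCSA is disclosed, no listed adverse event of special interest is cardiac, and even the vital-sign shift tables are optional. All of this stands, and it is why the point is minor.

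Two stronger readings are tempting, and the documents support neither.

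- A reader might infer that the trial cannot show whether dupilumab causes new ECG abnormalities. The placebo comparison, the adverse event tables and the paired readings in the database all tell against that. The limit is on what the SAP 5.8.5 table can count.
- A reader might infer that the SAP discarded a treatment-emergent ECG analysis promised in the protocol. The rule in Protocol 11.4.4 counts patients with any on-treatment PCSA and states no baseline condition. The protocol names a treatment-emergent PCSA table only for laboratory tests (11.4.4.2) and vital signs (11.4.4.3), and it has no ECG analysis subsection.

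What the reply does not answer is why ECG should lack the within-patient summary given to physical examination, when the coding and visits are the same.

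**Conclusion.** The point holds as a minor gap in descriptive safety reporting. No planned ECG summary compares a patient with his or her own baseline, and the by-visit table bounds the number of newly abnormal ECGs without identifying it. With 8 of 80 abnormal at both visits the range is 0 to 8 per arm. That count is an assumption; the lack of identification is not, and arises whenever some baseline abnormalities could have resolved by the later visit. The gap covers only new abnormal readings that fall short of the adverse event criteria. Efficacy, power and alpha are untouched.

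**What to change.** Keep the by-visit table in SAP 5.8.5 and add, in line with the treatment-emergent sentence in 5.8.4:

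- the number and percentage, by arm, of patients normal at baseline (the screening ECG) who have an abnormal ECG at any post-baseline assessment: Week 16, Week 28 or early termination, plus any unscheduled ECG if one was taken. Protocol 10.1.6 does not list ECG among the unscheduled-visit procedures, so few of these should be expected. With two-level coding, moving from normal to abnormal is the only form of emergence that can be recorded;
- a baseline-by-visit normal/abnormal shift table, by arm.

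Reconcile the remaining ECG wording in SAP 6.4 with SAP 1.3 and 5.8.

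The cost is one extra descriptive table from data already collected. No new assessment is needed, and sample size and testing do not change.

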5.8.6 Analysis of Immunogenicity Data

5.8.6.1 Analysis of ADA Data

The incidence of ADA response variables will be summarized using descriptive statistics in the ADA population. The NAb relevant analyses will be based on all patients in the ADA population with at least one non-missing NAb result (either “NAb negative” or “NAb positive”) after first dose of the IMP.

Frequency tables of the proportion of patients developing ADA positivity in the ADA assay, Neutralizing antibody status in the NAb assay, pre-existing immunoreactivity, treatment-emergent, treatment-boosted, persistent, indeterminate and transient ADA responses and titers will be presented as absolute occurrence (n) and percent of patients (%), presented by treatment groups. Percentages are rounded to 3 significant figures; therefore, there may be slight differences between subgroups and overall percentages.

Listings of anti-dupilumab antibody status, neutralizing status, and titers per time point and treatment group will be provided.

The following summaries will be performed on the ADA population:

- Number (%) of patients ADA negative at all time points analyzed by treatment group
- ADA titers using descriptive statistics (mean, standard deviation, geometric mean, median, minimum and maximum) by treatment group
- Number (%) of patients with neutralizing antibody status (negative or positive) by treatment group
- Number (%) of patients with pre-existing ADA, treatment-emergent ADA, and treatment boosted response ADA response by treatment group
- Number (%) of patients with persistent, transient and indeterminate treatment-emergent ADA response by treatment group

5.8.6.2 Immunogenicity and Pharmacokinetics

Potential associations between immunogenicity and serum concentration of dupilumab will be explored for dupilumab dose group. Plot of serum concentration of functional dupilumab may be provided for analyzing the potential impact of ADA/NAb status, ADA titer on PK.

5.8.6.3 Immunogenicity and Safety and Efficacy

Association of ADA responses and safety events may be performed in the ADA population.

The safety assessment will focus on the following events:

- Hypersensitivity (SMQ: Hypersensitivity [Narrow])
- Anaphylaxis (SMQ: Anaphylaxis [Narrow])

Number (%) of patients with the above mentioned safety events will be summarized by ADA status (positive or negative), and presence of neutralizing antibody (positive or negative).

In addition, the primary endpoint and key secondary efficacy endpoints will be summarized in patients with and without ADA (positive vs. negative) and neutralizing antibody (positive or negative) status if applicable.

5.9 Analysis of Pharmacokinetic Data

5.9.1 Descriptive Analysis of Dupilumab Concentrations in Serum

Serum concentrations of dupilumab will be summarized in the PK population using arithmetic and geometric means, SD, standard error of the mean (SEM), coefficient of variation (CV, %), median, minimum, first quartile, third quartile and maximum per sampling time by treatment group. If date and/or time of the drug injection and/or sampling is missing then the concentration will not be taken into account. Percentages are rounded to 3 significant figures; therefore, slight differences between subgroups and overall percentages may occur.

Concentrations of functional dupilumab below the lower limit of quantification (LLOQ) are set to zero. Line plots of mean (SD) and median functional dupilumab concentrations will be presented over nominal time (weeks; linear and log scales). Individual line plots of functional dupilumab concentration (spaghetti plots) will be presented over actual time (weeks) on linear and log scales. Individual scatter plots will be presented over nominal time (weeks). When the scale is linear, concentrations below the LLOQ are set to zero. In the log-scaled figures, concentrations below the LLOQ are imputed as LLOQ/2.

[figure not shown]
Dupilumab trough concentration on week 16 will be summarized based on baseline body weight categories (<70 kg, \geq 70-<100 kg, \geq 100 kg).

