10.1.5 Early Termination Visit

Patients who are withdrawn from the study before the primary endpoint visit (Week 16) will be asked to return to the clinic for 2 visits: once for early termination assessments, and again at Week 16 (primary endpoint visit), as described in [Section 10.1.2.6](#). Patients who are withdrawn from the study after the primary endpoint visit will be asked to return to the clinic for early termination assessments.

The following information will be collected:

- Concomitant medications/procedures
- AEs

The following procedures and assessments will be conducted:

- Pruritus NRS and pruritus categorical scale
- POEM
- DLQI
- EQ-5D
- Assess sick leave/missed school days
- Vital signs
- IGA
- EASI
- BSA
- Photograph AD area (select sites only)
- Weight
- Physical examination
- ECG
- Laboratory testing:
 - Hematology and chemistry

- Urinalysis
- Serum pregnancy test (WOCBP only)
[REDACTED]
[REDACTED]
- Functional dupilumab PK sample
- Anti-dupilumab antibody sample

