During the 16-week treatment period, patients will have study visits at Weeks 0, 2, 4, 8, 12, and 16. Safety laboratory tests, collection of samples for dupilumab concentrations and anti-drug antibodies (ADA), and clinical assessments will be performed at specified clinic visits as noted in the Schedule of Events ([Appendix 10.2](#)).

The end of treatment visit will occur at Week 16, 2 week after the last dose of study drug. The primary endpoint will be determined at Week 16.

Follow-up visits will occur every 4 weeks from Week 20 through Week 28. The duration of the 12-week follow-up period is based on the time expected for drug levels to reach below the lower limit of quantification in most patients after the last dose of dupilumab. The end of study visit will occur at Week 28.

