3.1 Intent-to-treat Population

The intent-to-treat (ITT) population includes all randomized patients. Efficacy analyses will be based on the treatment allocated by the interactive response technology (IRT) at randomization (as randomized). This is the primary analysis population for efficacy analyses.

For any patient who was randomized more than once, only the data associated with the first randomization will be used in any analysis population. The safety experience associated with any later randomization will be assessed separately.

Patients who temporarily or permanently discontinue from the IMP and who do not withdraw from the study will be asked to return to the clinic for all remaining study visits and complete all study assessments per the study schedule.

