3.4 Pharmacokinetic (PK) Population

The PK population consists of all patients in the safety population with at least one evaluable functional dupilumab concentration result following the first dose of study drug up to Week 16. Functional dupilumab concentration will also be reported in those patients who completed the study through week 28. Patients will be analyzed according to the treatment actually received.

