6.2 General Data Handling Conventions

For the laboratory safety variables and biomarker data, if the data below the lower limit of quantification (LLOQ) / limit of linearity, half of the lower limit value (i.e., LLOQ/2) will be used for quantitative analyses. For data above the upper limit of quantification (ULOQ) / limit of linearity, the upper limit value (i.e., ULOQ) will be used for quantitative analyses.

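### The dupilumab concentration table asks for geometric means but sets values below the LLOQ to zero, and the PK Week 16 window contains the whole Week 12 window

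*SAP*

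**What the plan says.** **Concentration summaries.** SAP 5.9.1 states that "Serum concentrations of dupilumab will be summarized in the PK population using arithmetic and geometric means", among other statistics, for each sampling time and treatment group. The rule for low values is "Concentrations of functional dupilumab below the lower limit of quantification (LLOQ) are set to zero", with no exception for the geometric mean. Two LLOQ/2 rules exist elsewhere. One is for plots: "In the log-scaled figures, concentrations below the LLOQ are imputed as LLOQ/2". The other, in SAP 6.2, is limited by its opening words, "For the laboratory safety variables and biomarker data", and so does not reach PK concentrations.

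**Where low values are expected.** SAP 4.6 schedules samples before dosing on Day 1 and at Weeks 12, 16 and 28, plus early-termination and unscheduled visits. SAP 2.3 explains that the 12-week follow-up is "based on the time expected for drug levels to reach below the lower limit of quantification in most patients" after the last dose. SAP 3.4 adds: "Functional dupilumab concentration will also be reported in those patients who completed the study through week 28".

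**Windows.** In the SAP 6.4 table for other variables, the PK/ADA column gives Week 12 as [2, 99] and Week 16 as [2, 155]. The windows map early-termination, unscheduled and EOT/EOS records. Scheduled visits are not windowed and take priority. Where several values fall in one window, the one nearest the target day is used.

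**The concern.** The zero rule and the geometric mean cannot both be applied in a cell that holds a BLQ value. The programmer must then report 0, report nothing, or let the software discard the zeros. In the last case the result describes quantifiable samples only, while the arithmetic mean beside it counts the BLQ samples as zero. The SAP recognises the log problem for figures but does not carry the solution to the tabulated statistic that needs it.

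The windows raise a different problem. Every day that qualifies for Week 12 also qualifies for Week 16, and the nearest-to-target rule chooses between values in one window, not between two windows for one value. A sample drawn early in treatment could be summarised as a Week 16 trough, including in the Week 16 summary by body-weight category. Trough concentration over time to Week 16 is the PK variable named in SAP 4.6, so this touches the main descriptive result for the systemic-exposure objective.

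**Working it through.** The plan gives no figure of its own to reproduce here.

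**1. Geometric mean with zeros.** GM = (x₁ × … × xₙ)^(1/n) = exp[(1/n) Σ ln xᵢ]. If any xᵢ = 0, the product is 0 and the mean log is minus infinity, whatever n is.

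As an illustration, take a simulated cell of 80 values (assumed log-normal, median 50, log-SD 0.5) with assumed LLOQs of 0.05 and 1.0. The SAP states no LLOQ.

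| BLQ values of 80 | Zero rule | Zeros discarded | LLOQ/2, LLOQ 0.05 | LLOQ/2, LLOQ 1.0 |
|---|---|---|---|---|
| 0 | 48.2 | 48.2 | 48.2 | 48.2 |
| 1 | 0 or undefined | 48.1 | 43.8 | 45.5 |
| 8 | 0 or undefined | 47.5 | 22.3 | 30.1 |
| 40 | 0 or undefined | 46.5 | 1.1 | 4.8 |

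Discarding zeros hides the BLQ samples almost completely. LLOQ/2 gives a finite value, but it depends heavily on the LLOQ once BLQ values are common, so the BLQ count has to be shown beside it.

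**2. Which sampling times are exposed.** Day 1 is pre-dose. Week 28 is 14 weeks after the Week 14 dose, when SAP 2.3 expects most patients to be below the LLOQ. Week 16 is possible: under SAP 3.1, patients who stop study drug but stay in the study "will be asked to return to the clinic for all remaining study visits and complete all study assessments per the study schedule", and Protocol 10.1.5 asks patients withdrawn before Week 16 to come back for that visit. A patient last dosed at Week 2 is 16 − 2 = 14 weeks off drug at Week 16, the same gap as 28 − 14 = 14.

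**3. Chance of at least one BLQ value at Week 16.** P = 1 − (1 − q)ⁿ, where q is the BLQ probability per patient. Both q and n are assumptions; 80 is the planned number per group.

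| q | n = 80 | n = 60 |
|---|---|---|
| 0.5% | 33% | 26% |
| 1% | 55% | 45% |
| 2% | 80% | 70% |
| 5% | 98% | 95% |

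**4. Windows.** [2, 99] holds 98 days and lies wholly inside [2, 155], which holds 154. Only 154 − 98 = 56 days (100 to 155) belong to Week 16 alone. The upper limits are midpoints between target days: (85 + 113)/2 = 99 and (113 + 197)/2 = 155. The Week 16 lower limit of 2 breaks that pattern; 100 would follow it. The columns for IGA, EASI, BSA, POEM and DLQI, for sick leave and for vital signs all end Week 12 on Day 99 and start Week 16 on Day 100.

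A Day 2 to 99 sample counted as Week 16 is 113 − 99 = 14 to 113 − 2 = 111 days early. Nominal dosing days are 1, 15, 29, 43, 57, 71, 85 and 99, so a sample taken before the Day 15 dose follows only 1 of 8 dosing occasions. If the scheduled Week 12 sample is also missing, the same sample can fill both visits.

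**The case against.** **On the geometric mean.** At Day 1 and Week 28, a geometric mean dominated by LLOQ/2 values tells the reader little, so the repair matters mainly at Weeks 12 and 16, where the documents predict no BLQ values. The Week 16 probabilities rest on assumed rates; 5% of 80 would mean about 4 patients, which nothing in the documents supports. Some software would return a finite value by discarding zeros. Using LLOQ/2 for one mean and zero for the other also puts two conventions in one table. These points are fair. The percentages are illustrative, and the table would need a footnote. The Day 1 and Week 28 cells are nevertheless specified outputs that the written rule cannot fill, and silent discarding is itself an unstated convention.

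**On the windows.** SAP 4.5.6 lists no Week 12 ADA analysis, so [2, 155] may suit ADA; the conflict is for PK only. The opening list of by-visit data in SAP 6.4 omits PK. Few records are exposed, because scheduled samples take priority and patients who stop early are asked to attend. The extracted table has a column with no heading. The limits on scope stand. However, the window table names PK in its heading, and both Week 16 entries in it read [2, 155], so the Week 16 reading does not depend on column alignment. The cell should still be confirmed in the original table.

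**Conclusion.** Both parts hold as written, and both are minor. The geometric mean cannot be reported meaningfully under the zero rule at Day 1 or Week 28, and a single BLQ value would do the same at Week 16. How likely that is cannot be derived from the documents. The window overlap affects only Day 2 to 99 early-termination or unscheduled PK samples used when the scheduled Week 16 sample is missing, a number the documents do not allow to be estimated. The arithmetic mean, median and quartiles generally remain usable. Protocol 11.4.5 plans no formal statistical analysis of PK, so no efficacy conclusion or error rate changes.

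**What to change.** - **SAP 5.9.1:** use LLOQ/2 for BLQ values when computing geometric means, as the SAP already does for log-scaled figures; report n (%) BLQ in every cell; and footnote that the arithmetic statistics use zero. Optionally, show the geometric mean as not calculable when more than half the values are BLQ. That threshold is a matter of judgement and does not come from the documents. With it, Day 1 and Week 28 would mostly show n (%) BLQ.
- **SAP 6.4:** give PK its own column with Week 12 as [2, 99] and Week 16 as [100, 155]. Set the ADA windows to match the visits at which SAP 4.5.6 analyses ADA. Check the current PK cell against the original table first.

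The cost is SAP wording and programming before database lock. No new data are needed.
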